- 133 • Unstable medical status
- 134 • Expecting an unstable baby requiring medical resuscitation
- 135 • Under the age of 18
- 136 • Non-English speaking requiring translation services

137 **Vulnerable Subjects**

138 Pregnant women may be considered vulnerable subjects. Teach back method during the
139 consent process will be used to ensure understanding regarding participation. This study
140 poses no medical risks to pregnant women, fetuses, or neonates. Any pregnant woman
141 appearing to be in a cognitive or emotional state that would prevent informed consent would
142 be excluded.

143 **Research Design and Methods**

144 If participating in the study in the experimental group the patient would watch the video prior to
145 delivery.

146
147 A sample size of 240 (120+120) will participate in this randomized control trial. Alternate
148 patients will be randomized at the time of admission into no video (Group A) and video groups
149 (Group B). 120 patients will be in Group A. 120 patients will be in Group B.

150
151 Randomization will occur in the order that they get enrolled into the study. If an eligible patient
152 wishes to participate in the study, the resident obtaining consent will consult the list of patients
153 to determine if that particular patient will be in Group A or Group B. The first patient enrolled
154 would be in Group A and asked a pre-survey regarding:

- 155 • their intention to practice skin to skin at the time of delivery
- 156 • if they participated in skin to skin in a previous pregnancy
- 157 • if they had any formal education about skin to skin
- 158 • if they did have formal education was it either
 - 159 ○ a.) Provided at a prenatal appointment,
 - 160 ○ b.) A formal class led by either a nurse or a lactation consultant.

161 The second patient enrolled would be in Group B and take the same pre-survey, immediately
162 watch “Jumping into Kangaroo Care”, and then immediately take the post survey which would
163 ask if they intended to practice skin to skin at the time of delivery. The third patient enrolled
164 would take only the pre-survey and be in Group A, etc.

165
166 The video the patients will watch is titled “Jumping into Kangaroo Care” by the Ohio Department
167 of Health. The video is 8 minutes and 52 seconds in length. The video discusses the benefits
168 and logistics of Kangaroo Care from professional’s perspectives and from new mother’s

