211 Participants may benefit by learning the benefits of skin to skin care after delivery.

212 **Potential benefits to others / contributions to knowledge**

213 Others can benefit by learning if video education video education can positively contribute to
 214 patients intent and compliance with skin to skin at the time of delivery

215 **Data Analysis**

216 Preliminary data on both primiparous and multiparous women from our records indicate that
 217 compliance with skin-to-skin is about 50%. We hypothesize that a 30% improvement in intention
 218 along with compliance with SCC is attainable with video education. We also have the ability to
 219 recruit 120 eligible women per group (240 in total) into the study. Using z test for two
 220 proportions, 90% power with alpha of 0.05, two-tailed, we will need about 53 patients per arm
 221 (106 in total) based on assumption that 50% of no formal education group and 80% of video
 222 education group would indicate their intention to participate, and hopefully participate in SCC
 223 post intervention.

224
 225 We will employ interim analysis, based on potentially recruiting 240 patients, and adopt “two
 226 looks”; one at the time when 120 (60 per group) women would be recruited and the other when
 227 240 (120 per group) women would be recruited. We will use cut-off points of $z=3.5$ for first look
 228 and $z=2.0$ for second look, as suggested by O’Brien-Fleming (1979), as decision rules to stop or
 229 continue data collection. If calculated z statistics is greater than 3.5 during first interim analysis,
 230 we will stop data collection. If calculated z-statistics is less than 3.5, we will continue data
 231 collection and reject the null during final analysis only when calculated z-statistics is greater
 232 than 2.0.

233
 234 Assuming 50% and 80% intention levels (30% difference in proportion) during first interim
 235 analysis, 50% interim sample size (120 patients) would result in absolute z- statistics of 4.89 to
 236 stop data collection.

237
 238 If data collection continues due to proportion difference less than 30%, sample size of 240
 239 during final analysis would produce absolute z-statistics of 2.20 to reject the null hypothesis
 240 based on assumption of 10% difference in end-point.

241
 242 Mean (Standard deviation) and sample size (percentage) will be used to summarize normally
 243 distributed continuous data and categorical data respectively. Either t-test of independence or

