 244 Chi-square test of independence will be used to test if significant differences exist between two
 245 groups on quantitative data or on categorical data respectively, at alpha of 0.05, two tailed. Z-
 246 test of two proportions would be used to test if significant differences exist between two groups.

247 Logistic regression would be used in order to account for other variables if necessary. SPSS
248 version 22 will be used to analyze data. [name], associated with Ohio University, will act as our
249 statistician and help us to analyze our data.

250 Data Monitoring to Ensure Safety of Subjects

251

252 Check if this study involves treatment or intervention and provide narrative of plan to
253 monitor data to ensure safety of subjects below:

254 The video intervention involves minimal risk.

255 Privacy Protections

256 We will collect coded data to ensure patient's privacy. We will also recruit and consent in
257 patient's private rooms on labor and delivery.

258 Data Storage and Confidentiality

259 Check all of the following which will be used to access (review), collect, receive, and/or
260 transmit study information:

- 261 **Email** **Camera/Camera Phone** **Portable media (flash drive, CD/DVD, hard drive, etc.)**
262 **Laptop** **Wireless Device** **Internet data access/data entry**
263 **Paper** **KHN Workstation** **Non-KHN computer**
264 **Other (specify):** [Click here to enter text.](#)

265 Describe where data/ records/ samples will be stored and how they will be kept secure:
266 Data will be stored in two binders on labor and delivery at the resident work station. Only
267 approved ob/gyn residents will have access to the study binders. One binder will have the
268 patient's name and enumber along with a number assigned to each patient. The other
269 binder will have the surveys with each survey having the number assigned to each patient.

270
271 Any email communication with PHI will be KHN only. If outside KHN email is needed it will
272 be encrypted. Internet data access will be through Epic. All electronic records will be stored
273 on the resident KHN workstation on L&D that is password protected and only accessible by
274 the PI.

275 Specify who will have access to study information/ to whom it will be released (if applicable):
276 Ob/gyn residents approved to participate in this study will have access to the study
277 information as they will help with the data collection

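### Covariate adjustment of the SSC-within-five-minutes comparison is left open, although suitable baseline items are collected in both groups; fixing one adjusted model costs nothing and may gain some power

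*Combined protocol and SAP*

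**What the plan says.** All references are to the combined protocol and SAP.

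- **Data Analysis, named tests.** A z-"test of two proportions would be used to test if significant differences exist between two groups". Just before that, t-tests and chi-square tests are to compare the "groups on quantitative data or on categorical data respectively, at alpha of 0.05, two tailed".
- **Data Analysis, adjustment.** "Logistic regression would be used in order to account for other variables if necessary". This is the only statement on adjustment. It gives no trigger, covariate list, endpoint, or rule for which result governs.
- **Data Analysis, decision rules.** The cut-offs of 3.5 (first look) and 2.0 (second look) apply to a z statistic. The first-look illustration is worded in terms of intention.
- **Research Design and Methods.** Before any video, both groups are asked about "their intention to practice skin to skin at the time of delivery", "if they participated in skin to skin in a previous pregnancy", and formal SSC education. Group B is asked about intention again after the video; Group A is not. Age, gestational age, complications, race, insurance and number of pregnancies are also recorded.
- **Purpose.** Intention is the primary endpoint. SSC within five minutes is the secondary one.

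**The concern.** For SSC within five minutes, the three pre-survey items are true baseline covariates: they are asked of every woman, before the intervention, in both groups. Whether a woman already intends SSC, and whether she has done it before, may well predict whether she does it now. If so, a comparison that ignores these items is less precise than one that uses them.

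The second issue is discretion. An adjusted analysis that is run only when judged necessary, with covariates not listed, can be decided on after the results are known. Two analyses of the same endpoint with no stated precedence give two chances of a significant result.

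**Working it through.** **1. The plan's own figure.** Inputs from Data Analysis: "50% of no formal education group and 80% of video" education group; "proportions, 90% power with alpha of 0.05, two-tailed, we will need about 53 patients per arm". With the pooled formula,

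n = [1.96·√(2·0.65·0.35) + 1.28·√(0.5·0.5 + 0.8·0.2)]² / 0.30² = (1.322 + 0.821)² / 0.09 = 51.0, so 52 per arm.

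This agrees with the stated 53. The sizing assumes no adjustment and needs none.

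**2. Unadjusted power for SSC within five minutes.** Control rate 50%, as Data Analysis reports for current compliance. Assumption: 90 evaluable per arm out of 120, because cesarean deliveries and 5-minute APGAR below 7 are left out of this comparison in a proportion not stated. Two-sided 0.05 (cut-off 1.96).

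- 50% versus 70%: (0.20 − 1.96·√(2·0.6·0.4/90)) / √((0.25 + 0.21)/90) = (0.200 − 0.143)/0.0715 = 0.80, which gives power of about 79%.
- 50% versus 80%: (0.30 − 1.96·0.0711)/0.0675 = 2.38, which gives about 99%.

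**3. What one baseline item can explain.** Suppose a share q of women intend SSC at baseline and intenders and non-intenders differ in SSC by g. Then R² = q(1−q)g² / (0.5·0.5), and the approximate gain in effective sample size is 1/(1−R²). With q = 0.5, R² = g²:

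- g = 0.2: R² = 0.04, factor 1.04
- g = 0.3: R² = 0.09, factor 1.10
- g = 0.4: R² = 0.16, factor 1.19
- g = 0.5: R² = 0.25, factor 1.33

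With q = 0.9, R² = 0.36g², so even g = 0.5 gives only 0.09 and a factor of 1.10.

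**4. Simulated power.** 90 per arm, average effect 20 points, 200,000 trials per cell, unadjusted z-test against a Mantel-Haenszel test stratified by baseline intention. Unadjusted power is about 79% throughout.

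| Gap, intenders vs non-intenders | Stratified: half intend, equal effect | Stratified: half intend, effect only in non-intenders | Stratified: 90% intend, equal effect |
|---|---|---|---|
| 0 to 10 points | 79% | not used | not used |
| 20 points | 80% | not used | not used |
| 30 points | 83% | 79% | 80% |
| 40 points | 86% | 80% | 81% |
| 50 points | 90% | 82% | 82.5% |

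For a 15-point effect (half intend, equal effect) the figures are 53% unadjusted and 57%, 61% and 66% for gaps of 30, 40 and 50 points.

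**5. Cross-check with logistic regression.** 120 per arm, the plan's cut-off of 2.0, one binary covariate with prevalence 50%, 5,000 trials per cell, unadjusted then adjusted power:

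- Gap 20 points: 33% to 35% (10-point effect), 62% to 64% (15), 87% to 88% (20).
- Gap 40 points: 33% to 38%, 63% to 71%, 88% to 92%.
- Gap 60 points: 33% to 47%, 63% to 82%, 88% to 97%.
- No association: no gain.
- At the planned 30-point effect, both analyses have at least 99.8%.

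**6. Type I error.** In the setting of step 4 with no true effect, the z-test alone rejects in 0.044 of trials and the stratified test alone in 0.049. Counting a trial as positive when either is significant gives 0.060 to 0.068 for gaps of 30 to 50 points.

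**Limits.** These runs use one binary covariate and do not model the interim look.

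**The case against.** The strongest reply is that a named unadjusted test is a valid choice, and that adjustment is a matter of efficiency. Much of this stands.

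- **Predictor strength is not documented.** A reader might infer that the pre-survey items are strong predictors. No figure supports this. The Background names delivery-room and hospital routines as obstacles, and the Methods record SSC not started for acuity, so the outcome depends partly on things that intention does not control. Previous SSC is also undefined for a first birth.
- **The protocol's hypothesis weakens the gain.** The Background places the effect in women who did not plan SSC. If it is confined to them, most of the gain disappears (step 4).
- **The sample size is not wrong.** A reader might infer that the trial as planned is short of power for want of adjustment. At 50% versus 80% nothing material is lost.
- **Data-driven modelling is possible, not planned.** A reader might infer that covariates will be picked by testing group differences at 0.05. The sentence on t-tests and chi-square tests does not mention logistic regression or baseline screening. Free choice among three or four covariates would give a type I error of roughly 7% to 16% in simulation, but the plan describes no such search.
- **Chance imbalance does not invalidate the z-test.** Its error rate already allows for it. Imbalance from predictable alternate allocation is a separate matter.

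One part of the reply does not stand. The 3.5 and 2.0 rules fix the z statistic, but the first-look illustration is framed on intention. For SSC within five minutes, nothing says whether an adjusted result could displace the z-test.

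**Conclusion.** The point holds as a conditional, low-cost improvement to the secondary endpoint, not as an error that undermines the trial. The plan leaves the trigger, covariates and standing of the logistic model unstated, while suitable baseline items are collected in both groups.

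The gain in power at a 20-point effect is about 1, 4, 7 or 11 points for gaps of 20, 30, 40 or 50 points (80, 83, 86 or 90 minus 79). This assumes 90 evaluable women per arm, half intending SSC at baseline, and the same effect in intenders and non-intenders. It falls to about 0 to 3 points if the effect sits only in non-intenders or if 90% already intend SSC, is about nil for gaps under 20 points, and is immaterial at the planned effect. The type I error of about 0.06 to 0.07 arises only if the more favourable of two analyses were reported, a practice that the documents do not describe.

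**What to change.** Replace the sentence on logistic regression in Data Analysis with one pre-specified analysis for SSC within five minutes: logistic regression on group, pre-survey intention (yes/no), previous SSC (yes / no / no previous birth) and formal SSC education (yes/no). State that this result governs for that endpoint and that the unadjusted z-test is supportive. Report the unadjusted difference in percentages alongside, since the adjusted odds ratio is a different measure. State that covariates are not selected by testing baseline differences.

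The model is small enough for the data. It has 1 + 1 + 2 + 1 = 5 terms besides the intercept. At 90 per arm and 50% versus 70% there would be 45 + 63 = 108 women with SSC and 72 without, or 72/5 = 14.4 of the rarer outcome per term.

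For the intention endpoint, keep the z-test as the statistic for the 3.5 and 2.0 rules. Do not use pre-survey intention as a covariate there: it is Group A's only intention measure and cannot be both outcome and covariate.

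The cost is a sentence or two in the plan and a few lines of SPSS, with no new data and no more patients. The downside is at most a negligible loss of power if the covariates do not predict SSC (79.5% to 78.7% at a gap of zero in the 90-per-arm simulation).

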INSTITUTIONAL REVIEW BOARD *at*
KETTERING
HEALTH NETWORK™

RESEARCH PROTOCOL

TO: Kettering Health Network Institutional Review Board

FROM: Principal Investigator: [name]
Phone Number / [contact]
Email Address: [contact]

DATE: 5/29/2017

STUDY TITLE: The Effect of Video Education on Skin-to-Skin at the Time of Delivery

VERSION # 1

1

2 Study Summary

3 The main purpose of this study is to determine the effect of prenatal video education on
4 pregnant women's intention to practice and actual practice of skin to skin contact (SSC)
5 after birth.

6 Purpose

7 This study hypothesizes that education in video format will increase patients knowledge
8 about skin to skin in a way that will make them consider participating in skin to skin
9 immediately after birth. Therefore our end point for this study is intention to participate in
10 SCC measured by a single questionnaire item "Do you plan on participating in skin to skin
11 (or kangaroo care) immediately after birth?" Our secondary end-point will measure whether
12 or not the patient was able to participate in skin to skin within five minutes of delivery.

13 Background and Significance

14 Despite strong support of breastfeeding by organizations such as the American Academy of
15 Pediatrics, the American Congress of Obstetricians and Gynecologists, and the American
16 Academy of Family Physicians, the rate of breastfeeding initiation at the time of delivery and
17 continuation at 6 months postpartum is below the Center of Disease Prevention's Healthy
18 People 2010 goals (1). UNICEF and the World Health Organization (WHO) have estimated
19 that if all babies were breastfed for a minimum of the first six months of their lives, the rate of
20 morbidity and malnutrition would significantly decrease all over the world (2). The benefits
21 of breastfeeding are numerous for both mothers and infants, with infants obtaining optimal
22 nutrition and passive immunity, and mothers obtaining a more rapid return of postpartum
23 uterine tone, postpartum weight loss, delay of ovulation, and decreased risk of breast,
24 ovarian, and endometrial cancers (3). As a result of this information, in 1991 WHO and
25 UNICEF launched the Baby-Friendly Hospital Initiative (BFHI) to encourage proper infant
26 feeding practices starting at birth. It is based on ten steps, which the hospital must meet
27 and maintain to obtain certification. In support of Step Four of the BFHI to "help mothers

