28 initiate breastfeeding within one hour of birth," the skin-to-skin variation of Kangaroo Mother
29 Care was initiated (4).

30

31 Kangaroo position, or skin to skin contact (SSC) on a mother's chest, provides
32 thermoregulation, physiological stability, appropriate stimulation, and encourages bonding
33 and breastfeeding (5). In fact, early SSC was significantly associated with type of feeding at
34 discharge through 3 months postpartum (6). Regrettably, according to the American
35 Academy of Pediatrics, some obstacles to SSC and breastfeeding include insufficient
36 prenatal education, disruptive obstetrical practices, and a lack of family and societal support
37 (7). Delivery room and postpartum hospital routines may also significantly disrupt early
38 maternal-infant interactions (8). These barriers to breastfeeding and SSC are more
39 prevalent amongst vulnerable groups, which includes low income, low educational level, and
40 black populations. While effective initiatives such as BFHI are present in hospital settings,
41 guidelines for primary care based interventions originating in a clinician's office currently do
42 not exist (3). Through encouraging education regarding SSC in a before the time of
43 delivery, patients can actively participate in SSC during delivery and advocate for early SSC
44 (9).

45

46 Education can easily influence behavior habits and does not need to require special
 47 difficulties on behalf of providers (9). In fact, educational programs have the single greatest
 48 effect of any single intervention on both initiation and short term duration for breastfeeding
 49 (3). Women who attended breastfeeding classes with lactation consultants - with or without
 50 video supplementation - had significantly increased breastfeeding at six months when
 51 compared to controls (1). Currently, common office practices include provision of written
 52 materials and discharge packets. Neither practice has been shown to be effective in
 53 increasing rates of breastfeeding. On the contrary, discharge packets have been shown to
 54 reduce the rates of breastfeeding (3). Ideally, breastfeeding education would use both
 55 individual or group sessions where both benefits of breastfeeding and SSC would be
 56 discussed (10). However, in a busy clinic setting filled with a vulnerable patient population,
 57 having the ability to get to extra educational classes is not always an option.

58

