59 Regardless of amount of prenatal education provided, Southview Medical Center will study
 60 participating patients at the time of admission for delivery who watch an 8 minutes
 61 second patient education DVD titled "Jumping into Kangaroo Care" by the Ohio Department
 62 of Health. Of importance, studies so far have shown no clear pattern for the outcome of
 63 breastfeeding in respect to intervention timing (7). In an analysis regarding video modeling,
 64 patients who viewed videotapes regarding treatment options had a greater understanding of
 65 the risks and benefits of those choices and were more apt to be active participants in
 66 decision making (11). Audio-visual material can also be entertaining and can be used by
 67 those who have limited literacy. Moreover, the information provided to patients on video has
 68 the advantage of being repeatable and consistent, which would allow us to provide the same
 69 information to all of our patients (12). By educating our patients in a video format at the
 70 beginning of their delivery admission, patients will have time to formulate questions and
 71 opinions to help them engage in an active dialogue with the staff that will be performing the
 72 delivery. The goal of educating mothers is not only to increase their knowledge and skills
 73 but also to influence their attitudes (13). By providing a video which models SSC to all non-
 74 emergent anticipated vaginal deliveries upon admission to the hospital, our hope is to
 75 encourage patients to actively participate in SSC at the time of delivery and become their
 76 own advocates.

77

78 The main purpose of this study is to determine the effect of prenatal video education on
 79 pregnant women's intention to practice SSC after birth. This study is critical for our hospital
 80 as quality measures for Southview Medical Center for quarter one of 2017 showed that we
 81 have only been 50% successful at initiating skin to skin in vaginal deliveries after 37 weeks
 82 gestation with a 5 minute APGAR of 7. Our goal as a hospital per BFHI is 82%. Our
 83 hypothesis is that 30% or more women who did not plan to use SCC would indicate their
 84 intention to use SSC post-intervention as compared to those who did not receive the
 85 intervention.

86 **Human Subject Population**

87 **Method of Subject Identification**

88 Patients will be recruited and consented to participate in the study at the time of admission

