278 Describe plans for storage, destruction, and/or return of study data and records after closure:
279 Study records will be stored with [name] and locked in her office at Kettering Hospital.
280 Paper records will be destroyed six years after closure of the study due to HIPAA
281 documentation being required. Paper records will be placed in confidential shredder bin for
282 destruction. Electronic records will be stored on [name] KHN workstation and
283 permanently deleted after six years.

284 Check if data or specimens will be saved or stored for future use and provide details:
285 [Click here to enter text.](#)

286 Estimated Period of Time to Complete the Study (after IRB Approval)

287 **Recruitment/data collection/active participation:** June 2017-December 2017

288 **Follow up:** N/A

289 **Data analysis/write-up:** January 2018

290 Consenting Process and Location(s)

291 **Initial consenting process**

292 The principal investigator and fellow ob/gyn residents will be involved in consenting of the
293 subjects. The consent will take place in private labor rooms on labor and delivery. The
294 consenting process is expected to take five to ten minutes.

295

296 **Consenting process after first visit**

297 N/A

298 **Documentation of consent (check all that apply):**

299 **Subjects' written, signed consent will be obtained.**

300 **Waiver of consent is requested (attach Consent Form – Application for Waiver*)**
301 *(Information is collected without subject knowledge: e.g. chart reviews)*

302 **Waiver of a signed consent is requested (attach Consent Form – Application for Waiver*)**
303 *(Individuals participate directly but do not sign a consent form: e.g. anonymous surveys)*

304 **Alteration of consent is requested (attach Consent Form – Application for Waiver*)**
305 *(Consent to be signed is not accurate or complete: e.g. study involving deception)*
306 **for non-exempt submissions*

307 Grant Application

308 N/A

309 Study Budget: Funding, Resources, and Expenses

310 **Resources needed**

- 311
 - Paper, binders, and video

312 **Expenses to be incurred**

- 313
 - Institutional Review Board administrative and review expenses

314

315 **Funding and sources of funds**

316 N/A

317 References

318

319 1. Rosen IM, Krueger MV, Carney LM, Graham JA. Prenatal breastfeeding education and
320 breastfeeding outcomes. *MCN Am J Matern Child Nurs.* 2008;33(5):315-9.

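### No one is masked for the five-minute skin-to-skin endpoint, and any approved resident can work out a woman's group from the two binders at the labor-and-delivery work station

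*Combined protocol and SAP*

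**What the plan says.** The endpoint at issue is the secondary one. Under Purpose, the protocol will record whether "or not the patient was able to participate in skin to skin within five minutes of delivery". The Background and Significance section accepts that this is not in the mother's hands alone: "Delivery room and postpartum hospital routines may also significantly disrupt early" contact between mother and infant.

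The residents' roles are spread over several sections:

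- **Consent.** Consenting Process and Location(s): "The principal investigator and fellow ob/gyn residents will be involved in consenting of the" women.
- **Allocation.** Under Research Design and Methods, the consenting resident checks a list to learn whether the woman is in Group A or Group B. Assignment strictly alternates. Group A completes a pre-survey only; Group B completes the pre-survey, watches the video and completes a post-survey.
- **Surveys.** Under Surveys / Interviews / Questionnaires, ob/gyn residents ask the questions in the labor room.
- **Data collection.** Under Data Storage and Confidentiality, approved residents help with it.

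The same storage section says "Data will be stored in two binders on labor and delivery at the resident work station. Only" and continues "approved ob/gyn residents will have access to the study binders. One binder will have the" patient's "name and enumber along with a number assigned to each patient. The other" "binder will have the surveys with each survey having the number assigned to each patient".

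Skin-to-skin times come from data the hospital already collects after delivery (Research Design and Methods). The protocol does not say who records or extracts them, or whether that person knows the group. It says nothing about blinding or masking of residents, delivery staff or data extractors. The storage section is concerned with confidentiality only.

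**The concern.** This is the trial's only behavioural endpoint, and the study summary names actual practice alongside intention as the purpose. A resident who knows that a woman saw the video could prompt her, or prompt the nurse, more readily than for a woman who did not. The recorded initiation time would then look the same whether the mother or the resident brought contact forward. Knowledge of group could also colour how a reason for non-initiation, or an exclusion for caesarean or low APGAR, is abstracted.

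The plan does not record who knew the group at delivery, so this could not be examined afterwards. It is a separate matter from bias in the answer to the intention question. It concerns care at birth and the ascertainment of the practice endpoint.

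**Working it through.** **Step 1. Can an approved resident work out the group?** Set three statements side by side:

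- Binder 1 gives name and study number.
- Binder 2 gives surveys by study number.
- Only Group B has a post-survey.

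Looking up the number and seeing whether a post-survey is present gives the group. No separate list is needed. If study numbers follow enrolment order, which is not stated, odd or even would also give it. The resident who enrolled the woman knows her group without any binder.

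**Step 2. The plan's own figure.** Data Analysis gives about 53 per arm for 50% against 80%, two-sided alpha 0.05 and 90% power. With pooled variance:

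n = [1.960·√(2·0.65·0.35) + 1.2816·√(0.5·0.5 + 0.8·0.2)]² / 0.30² = (1.322 + 0.821)² / 0.09 ≈ 51.0, rounded up to 52.

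This reproduces the stated figure to within a patient or two. The point does not depend on it.

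**Step 3. What a staff effect could do.** From the protocol: 50% base rate, 120 per group, final cut-off z = 2.0. Assumed, because the documents give no figure: a true video effect of zero; a net staff shift d in Group B (share of deliveries attended by an aware resident × effect in those deliveries, so 10 points in half of them is d = 5 points); and 80 evaluable per group as a lower case after the caesarean and APGAR exclusions.

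With p̄ = 0.5 + d/2, SE₀ = √(2p̄(1−p̄)/n) and SE₁ = √{[0.25 + (0.5+d)(0.5−d)]/n}:

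P(|z|>2.0) = 1 − Φ[(2SE₀ − d)/SE₁] + Φ[(−2SE₀ − d)/SE₁].

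Worked case, n = 120 and d = 0.05: SE₀ = 0.0645 and SE₁ = 0.0644. The upper tail is 1 − Φ(1.23) = 0.110 and the lower tail about 0.003, total 0.113.

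| Net shift d | 120 per group | 80 per group |
|---|---|---|
| 0 | 4.6% | 4.6% |
| 5 points | 11.3% | 9.0% |
| 10 points | 32.8% | 23.2% |
| 15 points | 63.9% | 46.7% |

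The protocol illustrates the z = 2.0 rule on intention. Applying it to the secondary endpoint is a further assumption.

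**The case against.** The strongest reply is that a video trial cannot be blinded and is not meant to be. Background and Significance wants women to form "opinions to help them engage in an active dialogue with the staff that will be performing the" delivery. Staff who respond to an informed mother are part of how the video is supposed to work, so some staff awareness is mechanism and not bias. That stands. It does not cover a resident who acts on the group list or binders without the mother having said anything, nor the person extracting the times. Neither needs to know the group.

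It is also fair to say that the binders are not the main route. The enrolling resident knows the group wherever the papers are kept, so moving them is not enough by itself. The routine hospital record as data source already gives some protection.

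A reader might infer more than the text supports:

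- **That the group list is in the binders.** Its location is not stated. The binders disclose the group anyway.
- **That residents on the study attend the deliveries and start skin-to-skin.** This is likely for ob/gyn residents with a work station on the unit, but no section says so.
- **That all unit staff can see the group.** Access is stated for approved residents only; nurses have none.
- **That the 82% goal gives a motive to favour Group B.** It is a hospital-wide goal and applies equally to Group A.
- **That differential care will occur, or is large.** The documents give no evidence on either.

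**Conclusion.** The concern holds in this form: approved residents can know the group, no one is masked, and the practice endpoint is open to delivery-room influence. If the plan is followed as written, a higher skin-to-skin rate in Group B could not be attributed to the video with confidence. This rests on the inference that some approved residents attend study deliveries.

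The size is unknown. Under the stated assumptions, a net 5- or 10-point shift raises the false-positive chance from 4.6% to about 11% or 33% at 120 per group, and to about 9% or 23% at 80. These figures show sensitivity and are not a forecast. The point touches the secondary endpoint, and the bias is only partly avoidable. It should be addressed because the protection is cheap and knowledge of group at delivery cannot be reconstructed later.

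**What to change.** 1. Keep the group list and completed surveys closed and away from the work station, opened only by the resident enrolling at that moment. Alternation across several residents still needs one running list, so the restriction is on when it is opened, not on a single holder. Keep the group out of the chart, the unit board and handover.
2. Extract skin-to-skin times, exclusions and reasons for non-initiation from the routine hospital record by study number, before group is linked.
3. Add a yes/no field: did the resident attending the delivery enrol this woman or know her group? Report it by arm as description only.
4. State that mothers and enrolling residents are unblinded, and limit the conclusion about practice accordingly.

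Do not make attribution depend on agreement with the subset of deliveries where the resident was unaware. Awareness arises after allocation and may come from the mother speaking up, so that subset could lose the very women in whom the video worked. It would also be imprecise: with 60 or 50 per group at 50%, the 95% margin is 1.96·√(0.5/60) ≈ 18 points or 1.96·√(0.5/50) ≈ 20 points.

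The cost is slightly less convenient record handling and one extra data field. Some unblinding through the enrolling resident and the mother will remain.
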